3.4 End of study

The study will end on the date the last patient completing the protocol.

4 Methods

4.1 Participant Selection and Withdrawal

Patients can be recruited from different cardiology clinics; at the end of an exercise test to record sinus tachycardia, and in the catheter lab during electrophysiological studies/ ablation procedures to record arrhythmias. Participants can withdraw from the study at any time and their standard care pathway will not be affected. If a participant decided to withdraw from the study at any point, we will continue to use any data collected up to withdrawal date.

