Statistical Methodology and Analysis	
400 patients are planned to be recruited as follows:
 
50 patients with supraventricular tachycardia (SVT) 50 patients with atrial flutter (AFl) 50 patients with atrial fibrillation (AF) 50 patients with ventricular tachycardia (VT) 50 patients with manifest pre-excitation 50 patients with sinus tachycardia to constitute the tachycardia control group
 
100 normal ECGs will also be collected from the first 100 patients who have regular sinus rhythm to constitute the sinus rhythm control group.
 
ECGs will be recorded in duplicate, with one recording being made using the AliveCor device, and one recording being made using a normal 12-lead ECG. Recordings will be undertaken as close to simultaneously as possible. The ECG diagnosis will be made by the lead Electrophysiologist on the 12-lead ECG so produced and this will be taken as the correct ECG diagnosis.
 
All ECGs (both 12-lead and AliveCor) will be reported by a Consultant Electrophysiologist, a General Cardiologist and a General Practitioner, blinded to the full study protocol and the patient allocation group. The output of the AliveCor algorithm for automatic ECG diagnosis will also be recorded. The readers will firstly read the AliveCor ECGs and at a later date read the 12-lead ECGs to prevent comparisons between the ECGs and to give accurate screening characteristics for AliveCor ECGs.
 
The diagnostic accuracy and screening characteristics of ECGs generated by the AliveCor device will be reported for each arrhythmia individually and in combination both by each reporter. To calculate screening characteristics, ECGs of sinus rhythm and sinus tachycardia will also be included in each analysis as normal controls. 95% confidence intervals will be calculated.
 
The primary end-point will be the sensitivity and screening characteristics of detecting each arrhythmia individually and in combination by each reporter using the AliveCor device, calculating 95% confidence intervals.
 
The binomial exact calculation would be used to calculate confidence intervals.
 
With a sample size of 50 patients with one arrhythmia, a sensitivity of 80% would produce a 95% confidence interval of 68.9% to 91.1%. With a sample size of 250 (all arrhythmias combined), a sensitivity of 70% would produce a 95% confidence interval of 64.5% to 75.1%, i.e. an absolute error of $\pm 5\%$.
 
The main secondary end-point will be to compare the sensitivity of a

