3.1.2 Study procedure

Every patient will be counselled about the project by a member of the Cardiology / Cardiology research team (doctor or qualified research nurse) and will be provided with a patient information sheet. Patients will be given up to 2 weeks to consider participation in the study. If in agreement, written informed consent will be obtained.

A 30-second ECG tracing will be obtained by simply holding the Smartphone and placing at least 1 finger from each hand on electrodes embedded into the back of the Smartphone case (figure 2). For sedated patients in the cath lab, AliveCor electrodes will be placed and taped on patient chest wall, left parasternal third intercostal space. A 12-lead ECG will also be recorded as near to simultaneously as possible. The 12-lead ECG will be reviewed by Principal Investigator (PI) to ensure that the ECG rhythm has not changed.

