4.2 Participant Recruitment and Screening

Patients with known positive ECG findings can be recruited from different cardiology clinics, following exercise testing, and in the catheter lab during electrophysiological study/ ablation.

Every patient will be counselled about the project by a member of cardiology / research team (doctor or qualified research nurse) and will be provided by a patient information sheet. Patient will be given choice to take up to 2 weeks to consider participation in the study. If in agreement, written informed consent will be obtained.

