4.5 Withdrawal of Participants

Participants can withdraw from the study at any time. This study is a diagnostic study and does not involve follow up visit.

5 Study Procedures

- List of patients details (name and DOB) with study number will be kept safely in a locked cupboard in research office, cardiac education centre, Blackpool Victoria Hospital. This can only be accessed by Principal Investigator and research team members.
- Each patient will be given ID 'for example AC-001'. For 12 lead ECG 'AC-ECG-001' and for AliveCor recording 'AC-AliveCor-001'.
- A 30-second ECG tracing will be obtained by simply holding the Smartphone and placing at least 1 finger from each hand on electrodes embedded into the back of the Smartphone case (figure 2). For sedated patients in the catheter lab, AliveCor electrodes will be placed and taped on patient chest wall, left parasternal third intercostal space. The AliveCor ECG tracing will be recorded as close to simultaneously as the 12 lead ECG recording as possible.
- All 12 lead ECGs will be anonymised and kept safely in locked cupboard in research office, cardiac education centre, Blackpool Victoria Hospital. This can only be accessed by Principal Investigator and research team members.
- All data will be stored anonymously on the Trust Server in a folder called 'AliveCor Study'. This will be password protected. Only PI will have access to this folder.
- All AliveCor traces (anonymised) will be sent electronically via secure trust enabled device to the PI who will store these traces on folder 'AliveCor Study' as described above.

Figure 2

6 Statistical Plan

Statisticians within the Sponsor organisation wrote and designed the sample size calculation and statistical description method.

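### The plan does not ensure any taped chest-wall controls or report by electrode placement, so pooled sensitivity and specificity may rest on different mixes of recording method

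*Combined protocol and SAP*

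**What the plan says.** There are two recording methods. By default the patient holds the device, "placing at least 1 finger from each hand on electrodes embedded into the back of the Smartphone case" (section 3.1.2). The exception, given in the Study Summary and in sections 3.1.2 and 5, is: "For sedated patients in the cath lab, AliveCor electrodes will be placed and taped on patient chest wall, left parasternal third intercostal space".

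Section 4.1 (and the Study Summary, Methodology / Design) links setting to rhythm. Besides cardiology clinics, patients can be recruited "at the end of an exercise test to record sinus tachycardia, and in the catheter lab during electrophysiological studies/ ablation procedures to record arrhythmias". Recording arrhythmias is the lab's only stated purpose. The wording is permissive: patients can be recruited in these places.

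For the other control group, the Study Summary (Statistical Methodology and Analysis) says "100 normal ECGs will also be collected from the first 100 patients who have regular sinus rhythm" and names no setting. For patients with abnormal findings, section 4.2 is broader: "Patients with known positive ECG findings can be recruited from different cardiology clinics, following exercise testing, and in the catheter lab".

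The Study Summary plans 250 abnormal and 150 control ECGs (100 sinus rhythm, 50 sinus tachycardia) and uses both control groups in each analysis. Section 6.2 reports by individual arrhythmia and for all combined, and the Study Summary adds reporting by reader. Neither matches or reports by electrode placement or setting.

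**The concern.** A chest-wall strip and a hand-held strip are different recordings. Section 2.1 describes the device as recording lead I through the fingers of each hand; the taped placement is somewhere else on the body, in a sedated patient. If taped strips occur mainly among cases, recording method travels with case status.

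The primary endpoint is sensitivity and screening characteristics for each reader. A pooled specificity drawn mostly or wholly from hand-held strips need not apply to the taped part of sensitivity. The pair, and any likelihood ratio built from it, may then describe neither way of using the device. Section 2.1 looks ahead to primary care, where recording would be hand-held.

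The tachycardia comparison is the most exposed. Sinus tachycardia is included as the control for fast rhythms, and its stated source is exercise testing, so those strips are hand-held. The SVT, flutter and VT strips set against them may be taped in any proportion.

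**Working it through.** No figure in the plan turns on this point, so there is none to reproduce. The check sets the texts side by side, then bounds the effect.

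**1. Which groups can be taped**

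| Group | n | Setting stated | Taped strips |
|---|---|---|---|
| Arrhythmia and pre-excitation cases | 250 | Clinics, exercise testing, catheter lab | Sedated lab patients only; share not stated |
| Sinus-tachycardia controls | 50 | End of an exercise test | None expected |
| Sinus-rhythm controls | 100 | None | 0 to 100 |

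If sinus tachycardia follows its stated setting, the taped share of controls is g = x/150, with x from 0 to 100. So g runs from 0/150 = 0% to 100/150 = 66.7%, and the plan fixes no value.

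**2. Taped share of cases**

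The taped share f of the 250 cases is not given, so the range is 0 to 250 strips. As one illustration only, if all SVT and VT strips and no others were taped, f = (50 + 50)/250 = 40%. The documents do not say this.

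**3. Effect of the mix on pooled specificity**

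Pooled specificity = s − g × d, where s is hand-held specificity and d is the loss of specificity on taped strips. Neither is in the documents. Assume s = 90% and d = 10 or 20 points.

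| Taped controls x | g | d = 10 points | d = 20 points |
|---|---|---|---|
| 0 | 0% | 90.0% | 90.0% |
| 25 | 16.7% | 88.3% | 86.7% |
| 50 | 33.3% | 86.7% | 83.3% |
| 100 | 66.7% | 83.3% | 76.7% |

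For example, with x = 50 and d = 10: 90 − (50/150) × 10 = 86.7%. The same readers and device could thus give pooled specificities 6.7 points apart (d = 10) or 13.3 points apart (d = 20), according to where sinus-rhythm controls happened to be recorded. For scale, the exact 95% interval for 135/150 (90%) is 84.0% to 94.3%.

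Sensitivity moves in the same way. If it differs by d points between placements, the pooled value departs from the hand-held value by f × d. At f = 40% that is 0.4 × 10 = 4 points or 0.4 × 20 = 8 points.

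**4. Whether reporting by placement is enough**

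The exact (Clopper-Pearson) 95% limits for k correct out of n are the 2.5% quantile of Beta(k, n − k + 1) and the 97.5% quantile of Beta(k + 1, n − k).

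- No taped controls: taped specificity cannot be estimated.
- 10 taped controls arising by chance, 9 correct: 55.5% to 99.7%, too wide to use.
- 50 reserved, 45 correct: 78.2% to 96.7%.
- The 100 hand-held controls that remain: 88.7% to 98.4% at 95/100, or 82.4% to 95.1% at 90/100. The latter compares with 84.0% to 94.3% at 135/150.

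Reporting by placement is needed, but it gives a usable taped specificity only if taped controls are secured in advance. All the observed proportions here are illustrative.

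**The case against.** A reader might infer that no control strip is taped, that every taped strip is a case, and that false positives on taped strips can never be seen. The documents do not support this. Section 4.1 is permissive and does not restrict the lab to arrhythmias. No setting is given for the 100 sinus-rhythm controls, two-thirds of the control group, and nothing bars a lab patient in sinus rhythm from being one. What stands is that taped controls are not ensured.

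Nor is sensitivity purely taped. Section 4.2 lets cases come from clinics and exercise testing, and unsedated patients hold the device. The two measures may overlap in method; they do not come from wholly different recordings.

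Three limits on the consequences are also right.

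- All three readers and the algorithm assess the same AliveCor recordings, so placement does not confound the differences between them. It affects only the mix of strips to which those differences apply.
- The planned precision statements and the non-inferiority comparison concern sensitivity, which uses no controls. Missing taped controls leave them untouched.
- That the look of a strip could cue a reader is conjecture. Readers are blinded to the full protocol and allocation group, and no feedback on diagnoses is described.

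The strongest point is against the remedy. Taped sinus-rhythm controls do not supply taped sinus-tachycardia controls. In the taped stratum, rate alone could separate fast cases from controls, and specificity could look better than it would against sinus tachycardia. That limit stands and has to be stated with the result.

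**Conclusion.** The concern holds in a limited form. Taping is confined to sedated lab patients, the lab's only stated purpose is recording arrhythmias, and sinus tachycardia is placed at exercise testing. With controls pooled and no reporting by placement, the plan followed as written can produce a specificity that does not apply to the taped part of its sensitivity.

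The size cannot be fixed from the documents: 0 to 100 of 150 controls and an unstated share of 250 cases may be taped. Under the assumed losses of 10 and 20 points, pooled specificity could shift by up to 6.7 and 13.3 points. If readers perform equally well on both kinds of strip, there is no bias, but the plan offers no way to show this.

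This should be changed before the sinus-rhythm group fills, since taped controls cannot be added to it afterwards without extra recruitment.

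**What to change.** 1. In the Study Summary (Statistical Methodology and Analysis) and section 6.2, record electrode placement for every strip and report sensitivity and specificity by placement. Compare hand-held cases with hand-held controls as the estimate for the device's intended use, and taped cases with taped controls separately.
2. In the Study Summary and section 4.1, state where sinus-rhythm controls are recorded. Reserve a fixed share of the 100 (for example 50) for consented, sedated catheter-lab patients while in sinus rhythm, one strip per patient, taped in the same way as the arrhythmia strips.
3. State beside the taped result that its specificity applies to sinus rhythm only, because that stratum has no sinus-tachycardia controls.

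The total stays at 400. The cost is that hand-held specificity rests on 100 controls instead of up to 150, and that control recruitment for the reserved share moves to the lab, among patients who are not also cases. Item 1 needs only one extra field on the case report form and added tables.

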4.1.1 Inclusion Criteria

1	Male or female patients
2	Age > 18
3	12 lead ECG finding of sinus rhythm, arrhythmia and manifest pre-excitation

4.1.2 Exclusion Criteria

1	Patients <18 years of age.
2	Patients unable to or unwilling to use the device.
3	Patients with cardiac pacemaker, ICDs, or other implanted electronic devices

4.2 Participant Recruitment and Screening

Patients with known positive ECG findings can be recruited from different cardiology clinics, following exercise testing, and in the catheter lab during electrophysiological study/ ablation.

Every patient will be counselled about the project by a member of cardiology / research team (doctor or qualified research nurse) and will be provided by a patient information sheet. Patient will be given choice to take up to 2 weeks to consider participation in the study. If in agreement, written informed consent will be obtained.

4.3 Randomisation Process

This is a diagnostic comparative study. No randomisation is required.

4.4 Informed Consent

Every patient will be counselled about the project by a member of cardiology / research team (doctor or qualified research nurse) and will be provided with a patient information sheet. Patients will be given up to 2 weeks to consider participation in the study. If in agreement, written informed consent will be obtained.

A copy of the consent form is included as an appendix.

4.5 Withdrawal of Participants

Participants can withdraw from the study at any time. This study is a diagnostic study and does not involve follow up visit.

5 Study Procedures

- List of patients details (name and DOB) with study number will be kept safely in a locked cupboard in research office, cardiac education centre, Blackpool Victoria Hospital. This can only be accessed by Principal Investigator and research team members.
- Each patient will be given ID 'for example AC-001'. For 12 lead ECG 'AC-ECG-001' and for AliveCor recording 'AC-AliveCor-001'.
- A 30-second ECG tracing will be obtained by simply holding the Smartphone and placing at least 1 finger from each hand on electrodes embedded into the back of the Smartphone case (figure 2). For sedated patients in the catheter lab, AliveCor electrodes will be placed and taped on patient chest wall, left parasternal third intercostal space. The AliveCor ECG tracing will be recorded as close to simultaneously as the 12 lead ECG recording as possible.
- All 12 lead ECGs will be anonymised and kept safely in locked cupboard in research office, cardiac education centre, Blackpool Victoria Hospital. This can only be accessed by Principal Investigator and research team members.
- All data will be stored anonymously on the Trust Server in a folder called 'AliveCor Study'. This will be password protected. Only PI will have access to this folder.
- All AliveCor traces (anonymised) will be sent electronically via secure trust enabled device to the PI who will store these traces on folder 'AliveCor Study' as described above.

Figure 2

6 Statistical Plan

Statisticians within the Sponsor organisation wrote and designed the sample size calculation and statistical description method.

6.1 Sample Size Determination

With a sample size of 50 patients with one arrhythmia, a sensitivity of 80% would produce a 95% confidence interval of 68.9% to 91.1%. With a sample size of 250 (all arrhythmias combined), a sensitivity of 70% would produce a 95% confidence interval of 64.5% to 75.1%, i.e. an absolute error of $\pm 5\%$.

The main secondary end-point will be to compare the sensitivity of a Consultant Electrophysiologist in detecting all arrhythmias using the AliveCor device *vs* the originally coded 12-lead ECG, to test whether the AliveCor device is non-inferior to the original 12-lead ECG diagnosis. Assuming a 95% one-sided confidence interval and a power of 80%, if there is a true difference in sensitivity in favour of the 12-lead ECG over an AliveCor ECG of 10%, and then a sample size of 301 arrhythmias would be needed to exclude a difference in favour of the 12-lead ECG of more than 16%.

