Methodology / Design	
Non-randomised open label diagnostic study
 
We are planning to record 250 pre-defined abnormal ECGs (50 each of atrial fibrillation, atrial flutter, pre-excitation, ventricular tachycardia, , supraventricular tachycardia) and 150 control ECGs (100 sinus rhythm, 50 sinus tachycardia) using both the AliveCor Smartphone device and a 12-lead ECG. All 400 ECGs will then be read by 3 blinded reporters – a Consultant Electrophysiologist, a Consultant General Cardiologist and a General Practitioner. The output of the AliveCor automatic detection algorithm will also be recorded as a fourth reporter. The screening characteristics of all 4 reporters using the AliveCor device vs the definitive 12 lead ECG will be analysed and compared.
 
Patients can be recruited from different cardiology clinics; at the end of an exercise test to record sinus tachycardia, and in the catheter lab during electrophysiological studies/ ablation procedures to record arrhythmias.
 
Every patient will be counselled about the project by a member of the cardiology / research team (doctor or qualified research nurse) and will be provided with a patient information sheet. Patients will be given up to 2 weeks to consider participation in the study. If in agreement, written informed consent will be obtained.
 
A 30-second ECG tracing will be obtained by simply holding the Smartphone and placing at least 1 finger from each hand on electrodes embedded into the back of the Smartphone case (figure 2). For sedated patients in the catheter lab, AliveCor electrodes will be placed and taped on patient chest wall, left parasternal third intercostal space. The AliveCor ECG tracing will be recorded as close to simultaneously as the 12 lead ECG

	recording as possible.
Duration	2 years
Participating Centres	Blackpool Victoria Hospital
Primary End Point	Screening characteristics and diagnostic accuracy of AliveCor ECG recordings to detect cardiac arrhythmias
Number of participants	400
Main Inclusion /Exclusion Criteria	
Inclusion:
 
 • Male or female patients >18 years with 12 lead ECG finding of arrhythmia, manifest pre-excitation, pacing rhythm, sinus rhythm or sinus tachycardia. 
Exclusion Criteria:
 
 • Patients <18 years of age. • Patients unable to or unwilling to use the device.

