6.2 Statistical Methods

The diagnostic sensitivity, screening characteristics and accuracy of the AliveCor device will be reported for each arrhythmia individually and for all arrhythmias combined, measuring 95% confidence intervals using the binomial exact method.

Non-inferiority will be assessed for each arrhythmia individually, and all arrhythmias combined for a Consultant Electrophysiologist reading the AliveCor generated ECG *vs* a near-simultaneously recorded 12-lead ECG.

The Chi-squared test and Fisher's exact test will be used to compare proportions. The McNemar test will be used to compare paired dichotomous dependent variables.

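### Neither planning interval in section 6.1 is the exact interval the plan specifies: the n=250 figure matches exact n=300, and the n=50 figure is a Wald interval

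*Combined protocol and SAP*

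**What the plan says.** Section 6.1 gives two precision statements for the primary endpoint, and the statistical entry of the Study Summary repeats them with the same figures.

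- Single arrhythmia: "With a sample size of 50 patients with one arrhythmia, a sensitivity of 80% would produce a 95% confidence interval of 68.9% to 91.1" per cent.
- All arrhythmias combined: "With a sample size of 250 (all arrhythmias combined), a sensitivity of 70% would produce a 95% confidence interval of 64.5% to 75.1" per cent, which the plan summarises as an absolute error of plus or minus 5%.

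The method is named in two places. In the Study Summary, directly before these two statements: "The binomial exact calculation would be used to calculate confidence intervals". In section 6.2, for the reported results: "measuring 95% confidence intervals using the binomial exact method".

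The combined sample size of 250 agrees with the design entry of the Study Summary, which plans five abnormal rhythm groups of 50 each.

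**The concern.** Because the Study Summary names the exact method immediately before the two intervals, a reader will take both as exact intervals at the stated n. The n=50 interval is symmetric about 80% (11.1 points each way), which an exact interval away from 50% is not. The n=250 interval has a total width of 10.6 points from its rounded limits, which is narrow for 250 observations at 70%.

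These intervals are the only quantitative support given for the size of the primary endpoint, which covers sensitivity for each arrhythmia and for all combined. If they are too narrow, the plan promises more precision than the design delivers. If the observed sensitivities equalled the assumed ones, the prespecified analysis would return intervals different from those in the plan.

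**Working it through.** **Inputs.** From section 6.1: n=50 at 80%, so x=40; n=250 at 70%, so x=175; stated intervals 68.9% to 91.1% and 64.5% to 75.1%. From section 6.2 and the Study Summary: exact binomial method, 95%, taken here as two-sided.

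**Formulas.**
- Exact (Clopper-Pearson): lower limit = Beta quantile at 0.025 with parameters x and n−x+1; upper limit = Beta quantile at 0.975 with parameters x+1 and n−x.
- Wald: p ± 1.96 × √(p(1−p)/n).

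**Step 1: reproduce the n=50 figure.** Wald: 0.80 ± 1.96 × √(0.80 × 0.20/50) = 0.80 ± 0.1109, which is 68.91% to 91.09%. This rounds to the stated 68.9% to 91.1%. None of the other variants tried gives it. The exact interval for 40/50 is 66.28% to 89.97%.

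**Step 2: try to reproduce the n=250 figure.** For 175/250:

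| Method | 95% interval (%) |
|---|---|
| Stated in plan | 64.5 to 75.1 |
| Exact | 63.91 to 75.61 |
| Wald | 64.32 to 75.68 |
| Wald, continuity-corrected | 64.12 to 75.88 |
| Wilson | 64.05 to 75.34 |
| Wilson, continuity-corrected | 63.84 to 75.53 |
| Agresti-Coull | 64.04 to 75.35 |
| Jeffreys | 64.11 to 75.43 |
| Mid-p | 64.10 to 75.44 |

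An exact interval at 90% rather than 95% gives 64.87% to 74.77%. None of these matches, so neither rounding nor a different choice among these methods explains the stated figure.

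**Step 3: look for an n that does reproduce it.** The exact interval for 210/300 is 64.47% to 75.13%, which rounds to 64.5% to 75.1%. A search over n from 200 to 419, with observed proportions near 70%, found a few other matches: exact 212/303, Wald 201/288, Jeffreys 203/290, and Wilson and Agresti-Coull 199/284. Only 210/300 combines the plan's own method with exactly 70%.

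**Step 4: size of the differences, in percentage points.**

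| | Stated | Exact at stated n |
|---|---|---|
| n=250, distance below / above 70% | 5.5 / 5.1 | 6.1 / 5.6 |
| n=250, total width | 10.6 from rounded limits (10.7 unrounded, as 210/300) | 11.7 |
| n=250, half-width | 5.3 (called 5) | 5.9 |
| n=50, distance below / above 80% | 11.1 / 11.1 | 13.7 / 10.0 |
| n=50, total width | 22.2 | 23.7 |

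At 70% sensitivity, an exact half-width of 5.0 points needs about 340 arrhythmia recordings (238/340 gives 5.00), against 250 planned.

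**The case against.** The strongest counter-argument has three parts.

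First, the n=50 interval is correctly computed as a Wald interval. Section 6.1 itself names no method, and planning with a normal approximation while analysing with an exact interval is not in itself a mistake. This stands in part: the n=50 figure is a mismatch with the named method, not an arithmetic slip. But the Study Summary names the exact method directly before both intervals, so the plan does present them as exact.

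Second, the shifts are small and nothing depends on them. The plan sets no target width or minimum lower limit, the group sizes are fixed at 50, and the exact method will be applied to the results whatever the planning text says. Measured against the plan's own interval and not its rounded 5%, the combined half-width moves only from 5.3 to 5.9. This stands as a limit on the size of the problem. It does not make the figures right, and they remain the only precision argument given for the primary endpoint.

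Third, n=300 as the origin of the error is inference. This also stands. Section 2.2 lists six rhythms, including paced rhythm, and six groups of 50 would make 300. No section gives a combined sample of 300, and other combinations of n and method give the same rounded limits. The finding needs only the fact that the stated interval cannot be obtained at n=250 by the specified method.

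**Conclusion.** The concern holds. The combined interval is wrong at n=250: the exact limits are 63.9% and 75.6%, so the stated lower limit is 0.6 points too high and the stated upper limit 0.5 points too low. The claimed error of 5% should read about 6%. The single-arrhythmia interval is not the exact one: the limits should be 66.3% and 90.0%, which lowers the lower limit by 2.6 points and the upper by 1.1. The two statements come from different methods, and one of them agrees with a different sample size.

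This rests on reading the plan's binomial exact method as the two-sided 95% Clopper-Pearson interval, and on counts of 40/50 and 175/250 for the assumed sensitivities. The practical effect is modest. No planned count changes automatically, and the final analysis is unaffected provided the exact method is used as written. The correction should still be made, because these figures are the stated basis for the size of the primary endpoint.

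**What to change.** In section 6.1 and in the statistical entry of the Study Summary, replace the two statements with:

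- n=50, sensitivity 80%: exact 95% CI 66.3% to 90.0% (13.7 points below and 10.0 above the estimate);
- n=250, sensitivity 70%: exact 95% CI 63.9% to 75.6%, an absolute error of about 6% (6.1 points below and 5.6 above).

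Name the exact binomial method in section 6.1, so that the planning figures and the analysis in section 6.2 visibly use the same one.

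The cost is two sentences in two places. There is no change to recruitment, data collection or analysis. The only downside is that the stated precision looks slightly less favourable.

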2.2 Study Objectives

Primary objectives: To assess the sensitivity and screening characteristics of AliveCor recording to detect a wide range of cardiac arrhythmias (AF, atrial flutter, SVT, VT, paced rhythm and pre-excitation) by 4 different readers.

Secondary Objectives:

- To test whether the AliveCor device will be non-inferior to the 12 lead ECG with respect to diagnosis of the arrhythmia when read by a Consultant Electrophysiologist.
- To compare the screening characteristics of the AliveCor's automated diagnostic algorithm with its screening characteristics when read by a Consultant Electrophysiologist, a general Consultant Cardiologist and a General Practitioner.

3 Study Design

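### The main secondary non-inferiority test in 6.1 uses the reference diagnosis as its comparator, and the stated sample size of 301 does not follow from that test

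*Combined protocol and SAP*

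**What the plan says.** The synopsis (Statistical Methodology and Analysis) fixes the reference standard. The diagnosis is "made by the lead Electrophysiologist on the 12-lead ECG so produced and this will be taken as the correct ECG diagnosis".

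The synopsis and 6.1 then describe the main secondary endpoint in the same terms. A Consultant Electrophysiologist's sensitivity for all arrhythmias on AliveCor is compared with "the originally coded 12-lead ECG", "to test whether the AliveCor device is non-inferior to the original 12-lead ECG diagnosis". The stated assumptions are a one-sided 95% interval, 80% power, a true deficit of 10 points for AliveCor and a margin of 16 points. The stated requirement is 301, which 6.1 specifies as arrhythmias. The planned number of arrhythmia recordings is 250.

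The other places are less specific:

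- The Methodology / Design row of the synopsis says that reporters' results on AliveCor against "the definitive 12 lead ECG will be analysed and compared".
- Section 2.2 asks whether AliveCor is "non-inferior to the 12 lead ECG with respect to diagnosis of the arrhythmia when read by a Consultant Electrophysiologist".
- Section 6.2 names only a 12-lead ECG recorded at nearly the same time, and does not say who reads it.

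The plan also produces a second 12-lead result. "All ECGs (both 12-lead and AliveCor) will be reported by a Consultant Electrophysiologist, a General Cardiologist and a General Practitioner", blinded, and "The readers will firstly read the AliveCor ECGs and at a later date read the 12-lead ECGs".

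**The concern.** If the comparator is the diagnosis that defines truth, its sensitivity cannot be anything but 100%, and only one proportion is left to estimate. The sample size for that problem differs from the sample size for a difference between two imperfect readings. The figure in 6.1 looks like the second kind, while the wording describes the first.

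Two things are at stake. First, 6.1 says 301 arrhythmias are needed while the plan collects 250, so the main secondary endpoint appears underpowered. Whether it is depends on which test is meant. Second, the decision rule differs. A fixed reference calls for a lower bound on one proportion, and a same-reader comparison calls for a bound on a paired difference.

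**Working it through.** **Inputs from 6.1:** one-sided alpha 0.05, power 0.80, true difference 0.10, margin 0.16. The distance to be resolved is 0.16 − 0.10 = 0.06. The documents give no sensitivity for either device and no discordance rate.

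**1. Reproducing 301.** For two independent proportions, n = (1.645 + 0.842)² × [p₁(1−p₁) + p₂(1−p₂)] / 0.06², with (1.645 + 0.842)² = 6.183 before rounding of the z values.

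| 12-lead / AliveCor (assumed) | Variance sum | n |
|---|---|---|
| 96% / 86% | 0.1588 | 272.7, so 273 |
| 95% / 85% | 0.0475 + 0.1275 = 0.175 | 300.5, so 301 |
| 94% / 84% | 0.1908 | 327.7, so 328 |
| 100% / 90% | 0 + 0.09 = 0.09 | 154.6, so 155 |

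The stated 301 appears at 95% versus 85%. These rates are back-solved.

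**2. Checking a paired formula.** With discordance ψ, n = 6.183 × (ψ − 0.10²) / 0.06², and 301 requires ψ = 0.185. The share missed only on AliveCor less the share missed only on the 12-lead is 0.10, and the two shares sum to 0.185. The share missed only on the 12-lead is therefore (0.185 − 0.10)/2 = 0.0425, and 12-lead sensitivity is at most 0.9575. On either formula, 301 presumes a 12-lead reading that misses arrhythmias.

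**3. The test as worded.** The comparator has sensitivity 1.00, so the null is AliveCor sensitivity ≤ 1.00 − 0.16 = 0.84 and the design alternative is 1.00 − 0.10 = 0.90. Normal-approximation sample sizes run from 155 (variance at 0.90 only) through 204 (null and alternative variances) to 231 (variance at 0.84 only). The exact binomial test gives:

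| n | Reject if at least | Power at 90% |
|---|---|---|
| 155 | 138 | 71.3% |
| 204 | 181 | 77.0% |
| 221 | 195 | 83.9% |
| 250 | 220 | 87.5% (actual size 4.7%) |
| 301 | 264 | 91.9% |

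Exact power moves in steps. It first reaches 80% at n=199 and stays above it from n=221. None of these routes gives 301.

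**4. What 250 delivers under each reading.**

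- Fixed reference: 87.5%, above target.
- Variance behind 301: power = Φ(0.06/√(0.175/250) − 1.645) = 73.3%, below target. The same formula at 301 gives 80.1%.
- Same-reader paired comparison, assumed scenarios only (simulated, Tango score test, 10-point difference): about 80% if the reader's 12-lead sensitivity is 98% and about 71% if it is 95%, with independent errors. If nothing is missed on the 12-lead alone, power is about 88% at either sensitivity.

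**The case against.** The strongest reply is that the plan is consistent where it is specific. The synopsis and 6.1 name the comparator in the same words, and 2.2 and 6.2 are shorter statements compatible with them. In 2.2 the phrase about the Consultant Electrophysiologist can attach to the AliveCor reading. This stands. A reader might infer that the sections contradict each other, but 2.2 and 6.2 are only silent on whose 12-lead reading is used. The McNemar test in 6.2 is a general listing for paired data and is not tied to this endpoint, so it does not show that a same-reader comparison was intended.

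A second reply is that 301 may rest on legitimate inputs that were not written down. This stands in part. The arithmetic of 301 may be sound for 95% versus 85%, but those inputs cannot belong to a comparator that is correct by definition.

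A third reply is that testing against the definitive 12-lead is a legitimate accuracy question, and that a figure that is too large does no harm. The first half stands. On the second, the excess figure makes an adequate plan look short.

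A reader might also infer that the test as worded is badly underpowered, because arrhythmias the reader would miss on both traces count against the device. Exact power at 250 would be 54.8% if AliveCor sensitivity were 88%, and 10.5% if it were 85%. Those cases place AliveCor 12 or 15 points below the reference, whereas 6.1 assumes 10, and the documents give no reader error rate. They do not measure a defect in the plan. Any such bias runs against the device.

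**Conclusion.** The point holds. As worded, the main secondary endpoint is a one-sample test against 84%, and 301 is the wrong number for it: 221 suffices for a stable 80% power, and the planned 250 gives 87.5%. These figures rest on the plan's own alpha, margin and 10-point assumption, and on the 12-lead diagnosis being correct by definition.

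That 301 came from 95% versus 85% with independent groups is an inference. Only if a fallible 12-lead reading was intended does 250 fall short, at about 73% on those inputs. A reader might conclude from 301 against 250 that the endpoint is underpowered; for the test actually written, it is not.

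This should be fixed, because the stated sample size does not match the stated test. It concerns a secondary endpoint and leaves the primary endpoint untouched.

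**What to change.** **If the coded reference is intended:** say so in the same words in the synopsis, 6.1 and 6.2. Call the test an 84% performance goal for AliveCor sensitivity, met when the one-sided exact 95% lower bound exceeds 84% (220 or more of 250). Replace 301 with the exact figures: n=221 for 80% power at 90% true sensitivity, and 87.5% power at the planned 250. This changes wording and one number, and needs no new data.

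**If a same-reader comparison is intended:** name the blinded Consultant Electrophysiologist's later 12-lead reading as the comparator, and score both readings against the reference diagnosis. Compare a one-sided 95% limit for the paired difference in sensitivity with the 16-point margin. State the assumed sensitivities, the discordance and the power of 250. The readings are already planned, so no data are added, but power may cost something: about 71% to 88% in the assumed scenarios above. The sponsor would have to accept that or add arrhythmias. The 12-lead also keeps some advantage, because the reference comes from the same trace and the 12-lead is read second.

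The choice is the sponsor's. It should be made, and the comparator named, before the readings are analysed.
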